Based on previously collected data, we expect that during our study timeframe around 260 women will meet eligibility criteria over the course of one year. The clusters will be randomly assigned by a biostatistician. This study, with 200 women enrolled (100 from intervention clusters and 100 from control clusters) will be powered to detect a change in Jadelle uptake rates from 3% to 15% at 85% power and 5% significance, with an intra class correlation of 2%.

[figure not shown]
Group	Proportion Positive	N Per Group	Standard Error	95% Lower	95% Upper
Population 1	0.03	100			
Population 2	0.15	100			
Rate Difference	-0.12	200	0.04	-0.20	-0.04

Alpha= 0.050, Tails= 2, Power = 0.848

Power computation: Normal approximation (unweighted mean p)
Precision computation: Log method

Phase II: Phase two of the study are six month and one-year follow-up visits that occur as part of routine care. Patients are immediately enrolled on delivery into Ninos Sanos, the early childhood health and development program offered through the CHD. Women and infants are seen monthly as part of the program, including routine visits at six and twelve months. At these sessions, mothers will be subject to a questionnaire regarding their contraceptive satisfaction and continuation habits, as well as whether or not they became pregnant since their delivery. This frequent and routine contact will ensure that patients are easily located for performing the follow-up questionnaire, but also will have no problem contacting study personnel if they have issues with their contraception or to report adverse events. We will also hold a focus group (interviews and surveys) for providers regarding their comfort and satisfaction with provision of care in the home setting before the study begins and after enrollment is complete.

Study Flow Diagram:

Study Visits: Patients who participate in the Community Health Services program through the CHD receive routine antepartum counseling on postpartum contraception in their home. At this visit, which is part of routine care, all women receive an educational intervention on contraception, which includes Jadelle® and the risks/side effects, benefits, and alternatives to the immediate postpartum implant.

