The same community health nurses who collect the database information and provide the clinical care will be trained in the consent, enrollment, and implant placement process for this study. During the postpartum visit, after a woman has completed her routine evaluation, the community health nurse will invite the woman to participate in this study. If she is not interested, it will not affect her involvement in the community program, she will receive care as usual. If she is interested, then the procedure for obtaining consent will be followed. While women can be enrolled in the clinical care database at any point during their pregnancy, the program entails four visits, ideally at <12 weeks, 13-28 weeks, 29-35 weeks, >36 weeks. During these visits information on health and pregnancy history are obtained as well as measurements of weight, fetal heart rate, fundal height, and blood pressure. Community health nurses come in contact with these women multiple ways: word of mouth, self-referral, referral through other CHD programs.

Procedures to Ensure Ethical Research: In order for the study to move forward as planned, it will require approval from numerous ethics organizations. These include the Colorado Multiple Institutional Review Board, the University Francisco Marroquin Institutional Review Board, and the Community Advisory Board for Research from the SW Trifinio region in Guatemala. These multiple levels of review will ensure that the research is culturally appropriate, that researchers are sufficiently qualified and expert to perform the proposed research, that the logistics of the international nature of the project are well planned and executed, and that dissemination of results back to the community is performed.

Patients are consented for this study at the postpartum visit. The patients participating in the cluster randomized trial will participate in a questionnaire at their six month and one year pediatric visits for the infant they delivered at enrollment into the study. Risks involved with the questionnaire are that patients may not want to answer questions about their contraceptive

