continuation, satisfaction, and pregnancy rates. They will have the option to leave the study at any point without any repercussions for their clinical care. We will have these questionnaires performed in a private location, in a one-on-one setting to increase comfort with discussing these issues, and patients will also be able to complete the questionnaire privately if they are literate and do not need assistance.

The primary foreseeable risk of all parts of the study is a breach of privacy and/or confidentiality. Study data will be stored securely in REDCap, which is HIPAA compliant and controls access on a study-by-study basis through the use of unique usernames and passwords. REDCap allows data fields to be flagged as identifiers, and investigators will utilize this feature to remove identifiers from datasets, which are exported for analysis.

Utilization of postpartum contraceptives, including placement of the implant how contraceptive use affects short interval pregnancy rates are the specific aims of this study; the study cannot be performed without offering contraceptives, including device placement. Fortunately, these medications are already in use in the study population and are non-experimental methods. Therefore, with proper counseling and informed consent, we believe the risks of the procedure will be acceptable to the patients and their partners.

Analysis Plan:

Methods & Models: The primary outcome of this study is contraceptive uptake rates in the intervention group. This study, with 200 women enrolled (100 from intervention clusters and 100 from control clusters) will be powered to detect a change in Jadelle uptake rates from 3% to 15% at 85% power and 5% significance, with an intra class correlation of 2%.

The satisfaction surveys will be administered at the six and twelve month well-child visits and will primarily assess patient experience with the medications, including side effects, continuation rates, and pregnancy rates. This quantitative analysis will provide direct feedback in terms of real-world use of contraceptives, their success rates, and their acceptability to the patients, which will also provide baseline research for future interventions to address issues surrounding patient choice of and satisfaction with different method of contraception, including the implant.

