Programs Used: The analysis plan for this will use summary statistics to describe the patient population as well as the outcomes. We will use Student t (normally distributed variables) or non-parametric medians (non-normally distributed variables) tests for continuous data and χ^2 or Fisher's exact tests (for variables with cell sizes <5) for categorical data. Bivariate analyses will be performed to compare the groups. Variables that are significant ($P < 0.05$) in the bivariate analyses will be included in a logistic regression to determine independent predictors of repeat pregnancy. SPSS statistical software (version 24.0.0; IBM SPSS Inc, Chicago, IL) will be used for all the analyses.

References:

2. Guttmacher Institute. Sexual and reproductive health of young women in Guatemala. Online 2014, accessed 1/17/17 (<https://www.guttmacher.org/sites/default/files/factsheet/fb-dd-guatemala.pdf>)
4. LARCs: IUD and Implant Options. Planned Parenthood. Accessed 1/23/17 (<https://www.plannedparenthood.org/planned-parenthood-mar-monte/patient-resources/long-acting-reversible-contraception/larc>)

Timeline: After we have obtained IRAC/COMIRB APPROVAL and Francisco Marroquin University Ethics approval to proceed with the study, we will begin the study. We anticipate the first step of the trial to start January 2018. We expect this to be a 24-month study; the timeline will appear as follows:

Months	Activities
Dec 2017	Training, Jadelle placement refresher course

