Jan – Dec 2018	Study Execution: Intervention in 3 study clusters, routine care in 3 study clusters
January 2019	Data analysis
Jan – Dec 2019	Follow-up Questionnaires: all participants
January 2020	Data analysis

Budget:

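### The primary uptake comparison is planned as individual-level bivariate tests, with no covariate adjustment and no allowance for six clusters; a two-stage adjusted cluster comparison would cost little and bring a modest gain

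*Combined protocol and SAP*

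**What the plan says.** Under Analysis Plan, Methods & Models: "The primary outcome of this study is contraceptive uptake rates in the intervention group". The sample-size statement there, repeated under Phase 1 of the Proposed Intervention, concerns implant uptake only: the trial is "powered to detect a change in Jadelle uptake rates from 3% to 15" per cent, with 100 women per arm and an intra-class correlation of 2%. The printed output reads "Alpha= 0.050, Tails= 2, Power = 0.848" and names its method as "Power computation: Normal approximation (unweighted mean p").

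Under Programs Used, the plan lists t or non-parametric tests for continuous data and chi-square or Fisher tests for categorical data, and adds that "Bivariate analyses will be performed to compare the groups". The only multivariable model is a logistic regression for repeat pregnancy, with covariates selected by bivariate P < 0.05. No covariate is named for uptake, and clusters are not mentioned in the analysis.

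The Timeline gives the allocation: "Study Execution: Intervention in 3 study clusters, routine care in 3 study clusters". Phase 1 says a biostatistician assigns the clusters at random and describes no matching, stratification or restriction.

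On the prenatal visits, Procedures for Data Collection & Quality Control says: "During these visits information on health and pregnancy history are obtained". The same section says that consent covers access to the pregnancy registry. Age (15–35) is an eligibility criterion.

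**The concern.** With only three clusters per arm, randomisation gives weak protection against chance differences in the women's characteristics, and the plan adds none in design or analysis. Age and parity may well be related to contraceptive choice. If they are, and they differ between the arms, the difference carries into this trial's uptake estimate, and variation in them between clusters adds to the between-cluster variance. The data needed to reduce this are already held, or can reasonably be inferred to be.

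The planned tests also treat 200 women as independent. Adjusting for covariates in an individual-level analysis would leave that error in place, so the remedy has to work at cluster level.

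**Working it through.** **Inputs from the documents.** Uptake 3% v 15%; 100 women per arm; 3 clusters per arm, so m = 100/3 = 33.3; outcome ICC 0.02; two-sided 5%.

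**Assumed, because the documents give no value.** The ICC of a covariate (0 to 0.10), and the strength with which age and parity predict uptake.

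**1. The plan's own figure.** Pooled normal approximation, with mean p = 0.09:

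z = [0.12 × √100 − 1.96 × √(2 × 0.09 × 0.91)] / √(0.03 × 0.97 + 0.15 × 0.85) = (1.2 − 0.793)/0.396 = 1.03, so power = 0.848.

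This matches the printed output exactly, with no design effect.

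**2. Clustering at the plan's ICC.**
- Design effect = 1 + 32.3 × 0.02 = 1.65.
- SE = 0.0396 × √1.65 = 0.051, against the printed 0.04.
- Effective n per arm = 100/1.65 = 60.7; power 0.640 by normal approximation, and 0.438 with a t-test on 6 − 2 = 4 df.
- A nominal 5% individual-level test has type I error 2 × [1 − Φ(1.96/√1.65)] = 0.127.

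**3. Chance imbalance in a standardised covariate.** SD of the arm difference = √{2 × [1 + 32.3 × ICC]/100}.

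| Covariate ICC | SD of arm difference | P(difference > 0.2 SD) |
|---|---|---|
| 0 | 0.141 | 16% |
| 0.02 | 0.181 | 27% |
| 0.05 | 0.229 | 38% |
| 0.10 | 0.291 | 49% |

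**4. Gain from adjustment, by formula.** Multiply the variance by (1 − R²), with R² assumed, ICC 0.02 and 4 df retained.

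| R² | Fall in SE | Power (4 df) |
|---|---|---|
| 0 | 0% | 0.438 |
| 0.02 | 1% | 0.445 |
| 0.05 | 2.5% | 0.455 |
| 0.10 | 5% | 0.475 |
| 0.20 | 11% | 0.518 |

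**5. Gain by simulation of the two-stage method.** Six clusters of 33, cluster log-odds variance 0.04, t on 4 df, mostly 3,000 trials per setting. The comparator is the unadjusted cluster-level t-test. Covariate effects are log odds ratios per SD.
- At 3% v 15%, for log-OR 0.5–0.8 and covariate ICC 0.05, the SD of the estimated difference falls about 2–5%, and up to about 10% at ICC 0.10. Power rises about 2–5 points. At log-OR 0.3 the SD falls by less than 2% and power rises about 1 point.
- At an assumed any-method uptake of 43% in control (assumed log-OR 0.8 for arm), for the same covariate effects and ICC 0.05, the SD falls about 6–14%; some runs gave 5–12%.
- With a covariate unrelated to uptake, unadjusted and adjusted power are 0.583 v 0.585 at 3% v 15%, and 0.468 v 0.470 at 43%.
- Under the null, rejection is 4.5–5.9%.

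A log-odds variance of 0.04 corresponds to an ICC of only about 0.04 × 0.15 × 0.85 = 0.005 at 15% uptake. The simulated powers are therefore higher than in step 4, and only the changes should be read from them.

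**The case against.** An unadjusted primary comparison is legitimate in a randomised trial. A reader might infer that imbalance biases the result. It does not in expectation; the harm is confined to the estimate from this one allocation.

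A reader might also infer that six clusters cannot balance age and parity. That is too strong: at a covariate ICC of 0.05, 62% of allocations (100 − 38) fall within 0.2 SD on a given covariate.

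A third tempting reading is that the plan gives up a lot of precision. The documents do not support it. They give no association between age or parity and uptake, no covariate ICC, and no any-method uptake rate. The larger gains come from an assumed control rate of 43%; the only planned effect is 3% v 15%, where the gain is about half or less. As planned, moreover, the tests overstate precision, because they ignore clustering, and that is the larger defect.

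Two further points stand. Parity is inferred from pregnancy history and age from eligibility; neither is named as a recorded item. And only about 3 + 15 = 18 implant users are expected, which limits the outcome model.

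A possible loss of power from adjustment applies to cluster-level covariates, which use up degrees of freedom: with 3 df and R² = 0, power is 0.374 rather than 0.438. Individual-level covariates in a first stage without arm keep the 4 df, so this does not count against the proposal below.

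**Conclusion.** The omission is real: uptake is to be compared by tests that neither adjust for anything nor respect the clusters, and nothing in the described allocation guards against imbalance. Imbalance large enough to matter is fairly likely, but far from certain.

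The benefit of adjustment itself is modest: a few per cent of the SD and a few points of power at the plan's own rates, more if the outcome is any-method uptake near one half, and nothing if the covariates do not predict uptake. All of these sizes depend on assumed prognostic strength and covariate ICC. The case for the change is that it costs almost nothing, and that its cluster-level second stage also corrects the inflated type I error.

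**What to change.** Make the primary uptake analysis a two-stage cluster comparison:
1. Fit a logistic model of uptake on individual-level age and parity, without arm.
2. Compute each cluster's mean residual (observed minus expected) and compare the six values between arms with a t-test on 4 df.
3. Report the unadjusted cluster-level comparison beside it.

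Name the covariates now, not by a P < 0.05 screen, and fix them before outcome data are analysed. With about 18 implant users expected, use no more than two. Confirm that both items are in the prenatal database. A permutation test alone will not serve: there are C(6,3) = 20 allocations, so the smallest two-sided P is 2/20 = 0.10.

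The cost is a change to the plan's wording, a few lines of code and slightly more analysis work. No new data collection is needed if both items are confirmed as recorded.

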Different methodologies have been used to try and increase uptake of contraceptives in the postpartum setting. One study looked at the provision of contraceptives in the home, and found that clients had less days not covered by effective contraceptive use during the 90 days following a first birth [5]. The authors suggested that home dispensing of hormonal contraceptives may improve women's postpartum contraceptive use and should be explored as an intervention in communities where contraceptives are not easily accessible [5]. This study design did not include offering LARC in the home.

A research group from the Department of Obstetrics and Gynecology at the University of Colorado wanted to observe the actual clinical impact that such LARC devices might have on repeat pregnancy and contraceptive continuation rates among adolescents [3]. They conducted a prospective observational study of immediate postpartum implant insertion and found a 2.6% pregnancy rate one year post-placement, compared to an 18.6% pregnancy rate among the control group [3]. Their research shows that high continuation rates of postpartum LARC can translate into reduced immediate postpartum pregnancy rates. Downstream benefits of using LARC in this population also appeared to include a 2-percentage point decrease in preterm birth, which was an unexpected but highly beneficial outcome [3].

This study combines the two prior aforementioned study in a new population; it desires to look at home-based provision of contraceptive care, including LARC in the form of the progesterone-only implant called Jadelle®, and observing how this reduction of a barrier to access increasing uptake of all contraceptives, including abstinence. The hypotheses are:

Hypothesis 1: Offering routinely available contraceptives in a home setting can increase incidence of contraceptive initiation in a postpartum rural Guatemalan population.

Hypothesis 2: Increased use of long-acting reversible contraceptives placed in the home setting in a rural, postpartum Guatemalan population will decrease short-interval pregnancy rates.

Research Objectives: This study has the following objectives:

Objective 1: Increase uptake of routinely offered contraceptives in the postpartum setting by providing them to women at their home-based postpartum visit.

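### The P<0.05 screen for the repeat-pregnancy model has no candidate list, does not define the groups compared and does not force in study arm; screened against pregnancy, it yields false predictors well above 5% of the time

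*Combined protocol and SAP*

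**What the plan says.** The rule is in the Analysis Plan, under Programs Used. Continuous variables are compared by a t test or a non-parametric test, and categorical ones by "χ^2 or Fisher's exact tests (for variables with cell sizes <5) for categorical data". The plan continues: "Bivariate analyses will be performed to compare the groups". It then says: "Variables that are significant ($P < 0.05$) in the bivariate analyses will be included in a logistic regression", the purpose being "to determine independent predictors of repeat pregnancy".

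This is the only multivariable model in the plan. The section does not say:

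- which variables are candidates, or how many there are;
- whether the groups are the two study arms or pregnant versus non-pregnant women;
- whether study arm stays in the model regardless of its p-value;
- how many terms the number of pregnancies can support;
- whether multiplicity, shrinkage or validation is considered, or whether the model is exploratory.

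Hypothesis 2 and Objectives 2 and 3 concern pregnancy by place of provision and by type of contraceptive, so arm and method are the factors of main interest for this outcome.

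**The concern.** Screening on a p-value and refitting the survivors in the same women uses the data twice. A variable that passes by chance tends to look significant again in the refit, whose p-values take no account of the selection. With several candidates, the chance that at least one noise variable is reported as an independent predictor can be many times the nominal 5%.

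The same rule can also discard what the study set out to examine. With few pregnancies and modest implant uptake, arm and implant use may miss P<0.05 even if their effects are real.

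At stake is the reading of the pregnancy results. Significance and Use of Results says that what is learned will feed further studies. Because the groups are undefined, two analysts could also fit different models from the same sentence.

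**Working it through.** **The plan's own figure.** The only computed figure is for uptake: "to detect a change in Jadelle uptake rates from 3% to 15% at 85% power and 5% significance", reported as "Alpha= 0.050, Tails= 2, Power = 0.848". With 100 women per group and mean proportion 0.09:

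power = Φ[(0.12√100 − 1.96√(2×0.09×0.91)) / √(0.03×0.97 + 0.15×0.85)] = Φ[(1.200 − 0.793)/0.396] = Φ(1.03) = 0.848.

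This reproduces the stated value. The documents give no figure for the pregnancy model.

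**Expected pregnancies.** No local rate is given. Background cites a North American adolescent cohort that "found a 2.6% pregnancy rate one year post-placement, compared to an 18.6% pregnancy rate among the control group". Combining those rates with 3% and 15% implant uptake, 100 women per arm:

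- control: 100 × (0.03×0.026 + 0.97×0.186) = 18.1
- intervention: 100 × (0.15×0.026 + 0.85×0.186) = 16.2
- total: about 34

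This is not a ceiling: 200 × 0.186 = 37, and the local rate could be lower or higher.

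**Number of candidates (assumed).** The protocol collects 12 side effects and two survey items (Ninos Sanos Visits) and four prenatal measurements (Procedures for Data Collection & Quality Control), 18 in all. It does not call these candidate predictors. Counts of 6 and 10 are shown as well.

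**Screen alone.** For k independent null variables, P(at least one passes) = 1 − 0.95^k: 26% for k = 6, 40% for k = 10, 60% for k = 18.

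**Screen against pregnancy, then refit.** Simulated trials had 200 women and no true predictors. Variables with P<0.05 entered a logistic regression, and a final P<0.05 counted as a false predictor. The main set used 1,000 trials per setting (standard error about 1.6 points); other sets varied prevalence and event count.

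| Candidates | At least one false predictor |
|---|---|
| 18 | 29–56% (roughly 30–55%) |
| 10 | 17–37% |
| 6 | 15–27% |

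For 18 candidates at a 17% pregnancy rate, the main set gave 56% (all continuous), 49% (6 continuous, 12 binary) and 37% (all binary, mostly rare). For the 6 + 12 mix, correlation of 0.3 between variables gave 40% and 0.5 gave 29%. Pregnancy rates of 10% and 5% (about 20 and 10 pregnancies) gave 41–46%, so event count matters less than candidate count.

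**Screen on study arm, then refit.** In the same simulation with 18 candidates, the false-predictor rate was 3.0% and 3.5% in two settings.

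**Do the factors of interest survive?** Under the cited rates:

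- Study arm, 18.1% versus 16.2% pregnant: passes an uncorrected χ² screen in about 6% of trials.
- Implant use, about 3 + 15 = 18 of 200 women, 2.6% versus 18.6% pregnant: passes the χ²/Fisher screen in about 37% of trials with 18 users fixed and about 32% if the number of users varies, so about a third.

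**Clustering.** These simulations ignore it. With six clusters of about 33 women and the protocol's intraclass correlation of 2%, assumed here to apply to pregnancy, the design effect is 1 + (33.3 − 1)×0.02 = 1.65. An unadjusted test of arm would then have type I error of about 2[1 − Φ(1.96/√1.65)] = 13%.

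**The case against.** The strongest objection is that the size of the problem rests on inputs the plan does not supply. This is largely right, and four stronger readings should be set aside.

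- A reader might infer that about 18 variables will be screened, so that a third to a half of such trials would mislead. No count is stated, and nothing makes the side effects candidates. Insertion-site pain, for instance, can arise only in implant users. With 6 candidates the rate is 15–27%.
- A reader might take 34 pregnancies as an upper limit. It is carried over from another population, and 37 follows from the same source.
- A reader might conclude that the refit gives no protection. In the simulations with 18 or 10 binary candidates, 66–84% of noise variables that passed the screen stayed significant, so 16–34% were removed. Protection is weak, not absent.
- In a two-arm trial, comparing the groups can naturally mean comparing the arms. On that reading the inflated rate does not apply and the figure is about 3%.

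The last point changes the fault without removing it. A screen on arm admits variables because they differ between arms, including ones measured after the intervention, and can omit strong predictors of pregnancy.

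It is also fair that the model is secondary. The primary outcome, under Methods & Models, is contraceptive uptake, which this rule does not touch.

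**Conclusion.** The concern holds in a conditional form. The selection rule is under-specified and unsound on either reading. If the screen is against pregnancy, the chance of at least one false independent predictor is well above 5% at every count examined, with the size set mainly by the assumed number of candidates and the correlation between them. If the screen is on arm, false predictors are rare but selection ignores the outcome.

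The loss of arm and implant use from the model under a pregnancy screen assumes the cited rates and the planned uptake; the local pregnancy rate is unknown. The direction of the problem is clear, but its exact size is not. It merits correction as an inexpensive improvement to a secondary analysis.

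**What to change.** Replace the P<0.05 screen with a short list of terms fixed before pregnancy outcomes are analysed, for example study arm, age and parity, all retained whatever their p-values.

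Set the number of terms by the observed number of pregnancies. Three terms give about 34/3 = 11 events per term at 34 pregnancies, but only about 3 at 10. If events are few, use penalised (Firth) logistic regression or fewer terms.

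Account for the six clusters when estimating the arm effect; forcing arm into an ordinary logistic model would leave the clustering error in place. Report odds ratios with confidence intervals and label the model exploratory. If bivariate tables are kept as description, state which groups they compare.

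The cost is a change of wording in the analysis plan, with no new data or participants. The downside is that fewer variables will be reported as predictors.

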Visit 1: At the postpartum visit in their home, patients will be enrolled in the study and provide informed consent. Once they have agreed to participate in the study, they will be offered postpartum contraception in the home in the intervention group, and through routine care (at CHD pharmacy or clinic location) in the control group. The nurses will bring all routinely available medications to the patient's home for those in the intervention clusters, including pills, condoms, Jadelle®, and depot medroxyprogesterone acetate. Patients who are breastfeeding will not be offered estrogen-containing methods. Participants in both the intervention group and control group will also be offered IUD placement; regardless of group, they will need to present to an area clinic setting for placement should they choose this method. Women opting for Jadelle® will receive immediate implant placement, and women that opt for other methods will receive their method of choice. 99% of patients in the community service program are seen for this postpartum visit, which is part of the standard of care for patients in this region.

Ninos Sanos Visits: The follow-up visits will occur through routine care as part of the Ninos Sanos program, into which all patients in the Madres Sanas program are automatically enrolled. Mothers are seen with their infants monthly in their home, including visits at six and twelve months after delivery. At these routine visits, the mothers enrolled in the study, in both groups, will complete a survey. The surveys will assess patient continuation rates and satisfaction with the contraceptive method of choice. Patients will also be queried about side effects such as: irregular bleeding, weight gain, headaches, rash, chest pain, moodiness, insertion site pain, cramps, acne, nausea, hair loss, or issues with breastfeeding after device placement. All patients will be questioned regarding repeat

pregnancy at these visits, as well, including outcomes of repeat pregnancies such as delivery, termination of pregnancy, or spontaneous abortion. We anticipate that this survey will take about 10 – 20 mins to administer. Additionally, the study nurses will perform a survey of their comfort and satisfaction with administering contraception in the home, which will be performed after enrollment is complete. These questionnaires are included with the submission.

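### The repeat-pregnancy model admits any variable with P<0.05 and sets no time order, so it can report a consequence of pregnancy, or an item of unknown order, as an independent predictor

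*Combined protocol and SAP*

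**What the plan says.** The rule is in the Analysis Plan under Programs Used. The screening step reads "Bivariate analyses will be performed to compare the groups", and the groups are not defined there. Variables reaching P<0.05 "will be included in a logistic regression to determine independent predictors of repeat pregnancy". The wording makes entry mandatory for a significant variable. There is no candidate list, no restriction to baseline variables and no rule on time order.

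The likely candidates are described under Study Visits (Ninos Sanos Visits). On the six- and twelve-month surveys: "The surveys will assess patient continuation rates and satisfaction with the contraceptive method of choice". On symptoms: "Patients will also be queried about side effects such as: irregular bleeding, weight gain, headaches, rash, chest pain, moodiness, insertion site pain, cramps, acne, nausea", followed by hair loss and breastfeeding problems, 12 items in all. The outcome is asked at the same visits: "All patients will be questioned regarding repeat" pregnancy, including pregnancies that have already ended. Methods & Models confirms that one set of surveys supplies all of this, since they "will primarily assess patient experience with the medications, including side effects, continuation rates, and pregnancy rates".

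The Phase II text frames the outcome as any pregnancy since the index delivery. No date of conception, of stopping a method or of symptom onset is described.

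**The concern.** A predictor should be known before the event it predicts. Several items in the surveys may instead follow from pregnancy. Nausea, weight gain, cramps, moodiness and breastfeeding problems can be symptoms of a new pregnancy, and a woman who conceives may stop her method because she has conceived. If such an item enters the model, its odds ratio describes the effect of pregnancy on the item, yet the plan would call it an independent predictor of pregnancy.

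Continuation raises a second problem. Home provision is meant to lower pregnancy rates through uptake and continued use. If assigned arm and continuation are both in the model, the arm coefficient no longer carries the whole effect of the intervention.

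This is the only multivariable analysis in the plan, and its outcome is the one named in Hypothesis 2 and in Objectives 2 and 3. Its results are likely to be read as guidance on which women are at risk.

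**Working it through.** **1. The plan's own figure.** The plan gives no figure for this model. Its only computed design figure is power 0.848 for implant uptake of 3% v 15% with 100 per arm. It reproduces without any clustering allowance: Φ[(0.12 − 1.96×√(2×0.09×0.91/100)) / √((0.03×0.97 + 0.15×0.85)/100)] = Φ[(0.12 − 0.0793)/0.0396] = 0.848. It concerns uptake and is not used below.

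**2. Number of pregnancies.** The documents call the local birth interval, and the pregnancy rate among local implant users, unknown (Problem). The Background cites one-year rates of 2.6% with an implant and 18.6% in controls from a North American study of adolescents. Applying these to the uptake rates in the power statement, and giving every woman without an implant the control rate:
- Intervention: 100×(0.15×0.026 + 0.85×0.186) = 0.39 + 15.81 = 16.2
- Control: 100×(0.03×0.026 + 0.97×0.186) = 0.08 + 18.04 = 18.1
- Total: about 34 of 200

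Because the local rate may be lower, 10 and 20 pregnancies (5% and 10%) are also shown, with 5 (200×0.026 = 5.2) as a low extreme.

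**3. Screen on pregnant versus not pregnant.** Let k women have become pregnant. A symptom is reported by a proportion p of them and by 8% of the other 200 − k (both assumed). The chance of passing is the sum, over a ~ Bin(k, p) and b ~ Bin(200 − k, 0.08), of the probability of each table with Fisher P<0.05. The odds ratio is [p/(1−p)]/[0.08/0.92].

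| p in pregnant women | Odds ratio | k=5 | k=10 | k=20 | k=34 |
|---|---|---|---|---|---|
| 8% (unrelated) | 1.0 | 1.9% | 2.5% | 2.7% | 3.4% |
| 20% | 2.9 | 11.9% | 23.1% | 37.1% | 48.2% |
| 30% | 4.9 | 25.5% | 49.6% | 74.0% | 87.4% |
| 40% | 7.7 | 42.1% | 73.5% | 93.5% | 98.7% |

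**4. Does the item survive the regression?** A simulation (800 trials per setting, N=200) assumed the item in 10% of non-pregnant women, screened it, and then fitted logistic regression on arm and item. With 50% of pregnant women reporting it, the item passed the screen and was significant in the model in about 77%, 96% and over 99% of trials at pregnancy rates of 5%, 10% and 18.6% in women without an implant. With 30% reporting it, the figures were about 42%, 58% and 77%. Adjusting for arm gives little protection.

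**5. Screen by arm.** With the step 2 rates and 40% v 8%, expected nausea is:
- Intervention: 0.162×0.40 + 0.838×0.08 = 13.2%
- Control: 0.181×0.40 + 0.819×0.08 = 13.8%

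With 100 per arm this passes in about 3% of trials by Fisher's test (about 5% by chi-square), which is chance level. Items tied to the method, such as continuation or insertion site pain, could still differ by arm, because the intervention aims to change which methods are used. The documents give no figures from which to size that route.

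Clustering is ignored in steps 3 to 5.

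**The case against.** The strongest reply is that the plan never names survey items as candidates. Objectives 2 and 3 list pregnancy, satisfaction and continuation together as rates to be determined, and Objective 4 documents side effects, so the authors may regard all of them as outcomes. The groups named in those objectives are home versus routine care and long-acting versus short-acting methods. Pregnant versus not pregnant is not named, and on an arm screen a pure pregnancy symptom enters only by chance. The questionnaires were submitted separately and may contain dates.

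Much of this stands, and it rules out four stronger readings that a reader might infer:
- That consequences of pregnancy will be reported as predictors. The documents support only that they can be. It depends on the items being screened and on which groups are meant.
- That stopping a method is simply a result of pregnancy. It can come first and be a genuine cause. The Background itself links high continuation to fewer pregnancies. The defect is that the order is not established.
- That hardly any woman can be both pregnant and continuing, so that the fit must fail. The outcome is any pregnancy since delivery, including ended ones, and such women may be using a method again. Separation is a possibility only.
- That Hypothesis 2 will be judged on this model. The stated chi-square or Fisher tests can compare pregnancy rates between groups, and the primary outcome is uptake.

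What the reply does not remove is the rule itself. Inclusion is mandatory for a significant variable, nothing excludes the survey items, and each reading of the groups leaves a route in: consequences of pregnancy on one, items on the path from arm to pregnancy on the other.

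**Conclusion.** The point holds as a fault in the rule for a secondary model. Followed as written, the plan allows a consequence of pregnancy, or an item of unknown time order, to be labelled an independent predictor, and allows adjustment for continuation to take away part of any arm effect.

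The size is uncertain. On a pregnant-versus-not screen with 10 to 34 pregnancies, the chance that one such symptom passes runs from 23–48% through 50–87% to 74–99% as its assumed prevalence in pregnant women goes from 20% to 30% to 40%, against 8% in the others. An unrelated item passes in about 3%. All the prevalences are assumptions, and the upper event count borrows rates from another population. On an arm screen the symptom route closes, and only the method-related route remains. The change should be made, but the analysis of uptake does not depend on it.

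**What to change.** In the Analysis Plan under Programs Used:
- Replace the P<0.05 screen for this model with a short pre-specified list fixed before any conception: assigned arm, age, pregnancy history and breastfeeding status at Visit 1.
- Put the method chosen at Visit 1 in a separate second model, because it lies between arm and pregnancy.
- State that continuation, satisfaction and side effects from the six- and twelve-month surveys are outcomes, and enter the repeat-pregnancy model only if dated before conception.
- Define the groups for any bivariate comparisons that remain.

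Keep the list short. Four terms mean 8.5 pregnancies per term with 34 events (34/4) but only 2.5 with 10 (10/4), so the plan should say which terms go first if events are few.

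The cost is a few sentences of analysis text and no extra patients. Age is an eligibility criterion and pregnancy history is already collected at the prenatal visits. Breastfeeding status has to be known at Visit 1, because it limits which methods are offered; the sponsor should confirm that it is recorded. The downside is that the model no longer explores associations within the same survey. Those can still be reported descriptively.
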